### ***Veteran involvement and Characteristics***

This 4-site research project aims to implement and evaluate the CV toolkit designed to increase identification of CV risk among women Veterans, enhance patient/provider communication about CV risk, and increase women Veterans engagement and retention in relevant health services including referrals to key health programs. We will recruit adult women Veterans who visit their women's health provider at one of the four study sites if a CPRS CV risk template was activated from their primary care visit or they attended the Gateway to Healthy Living program. As long as the woman Veteran patient is also able to give informed consent to complete our protocol, she is eligible to participate. We expect to approach up to 200 women Veterans per site over the study period in order to achieve a minimum of 65 women participants in the survey/interviews for CV toolkit at each site. Our goal is to have 260 women total (minimum 65 per site across 4 sites) engaged in the project over the course of the study. Participation includes a brief survey at baseline and six-month post-baseline, and for a subset of women, a brief qualitative interview (approximately every third consented woman with a completed survey will be approached for an interview for a minimum of 20 patient interviews at a site). Women will be consented at the time of the survey and interviews. The women will also be consented to link their responses to their medical records at the time of the survey.

We will also use medical record data (CPRS template data and CDW data) to evaluate the roll-out of the intervention and the referral rates at all sites. This data will be evaluated for all women patients seen by the providers in the study over the study period. The data will only be evaluated in the aggregate and will not be linked to the patient survey or interview data (unless medical record access consent is received at the time of the survey).

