**Power Analysis:** Our goal with the power analysis was to ascertain the number of providers who would need to “turn on” the intervention (i.e., the number of PCPs who use the CV template, as well as the minimum number of patients that would need to be exposed to the care model. Consistent with our nonrandomized stepped wedge design, the power analysis presented here is for a 3-level hierarchical linear model where patients are clustered within PCPs within sites. In the final analysis structure, patients are the Level 1 units, the timing of PCP template use/referrals represents Level 2 units, and sites are the Level 3 units. The outcome of interest for CV Toolkit is the number of referrals to services (e.g. *Gateway to Healthy Living* and other services). The outcome is binary (referred/retained vs. not), and measured at the patient level (Level 1). Treatment effect is measured at Level 2, i.e., timing of when the PCPs turn on. Parameters required for calculating power are: alpha ( $\alpha$ ) = 0.05, sample size of patients clustered within referring PCPs ( $n$ ) = at least 260 (based on prior work), the number of sites ( $K$ ) = 4, the Plausible for Retention among those with low utilization (PI) = 5% to 85%, and Effect Size Variability (ESV) = medium or 0.05. Based on the resulting power curve, we need at least 8.78 (rounded to 9) referring PCPs per site to achieve power at 0.80. Our power analyses assume that the treatment effect is linear over time, i.e. patients that are retained longer have proportionally better outcomes. While selected details of the resulting dose response curve may vary, sensitivity analyses demonstrate a reasonable approximation enabling detection of treatment effects.

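### The 0.80 power with nine PCPs per site rests on a retention input for low utilisers, so it is not established for the planned analysis of referral among all women seen

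*Combined protocol and SAP*

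**What the plan says.** The Power Analysis paragraph of section 5.6 describes a three-level model. It names referrals to services as the outcome of interest, then defines the binary event as a composite of referral and retention. Its inputs are:

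- alpha of 0.05, and a patient number given as "at least 260 (based on prior work");
- four sites;
- for the event rate, a range: "the Plausible for Retention among those with low utilization (PI) = 5% to 85" (per cent);
- for the variability of the effect, a single value: "Effect Size Variability (ESV) = medium or 0.05".

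The result is that "we need at least 8.78 (rounded to 9) referring PCPs per site to achieve power at 0.80". The paragraph adds that the effect is taken as linear over time, with women retained longer doing proportionally better.

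The analysis is described elsewhere. Section 5.6 (Quantitative Analysis) models the toolkit's effect on referral rates. Section 5.1 (Nonrandomized Stepped Wedge Study Design) measures outcomes in all patients at each site and compares control with intervention periods. Of the medical record data, section 5.1 (Veteran involvement and Characteristics) says: "This data will be evaluated for all women patients seen by the providers in the study over the study period". The same section sets the survey target: "Our goal is to have 260 women total (minimum 65 per site across 4 sites").

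**The concern.** A power figure belongs to one event in one population. Here the rate input carries the label of a different event (retention) in a subgroup (low utilisers) that no recruitment or eligibility text selects. Survey entry under section 5.1 needs template activation or Gateway attendance, plus ability to consent. Section 5.2 adds the first visit in the implementation period, and section 5.4 lists staff criteria only.

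The nine-PCP figure and the 0.80 power are the only stated justification of size for the stepped wedge evaluation. Site Selection admits clinics on a minimum of four to eight qualifying PCPs, so whether nine are needed has practical weight. If the referral result is null, a reader will want to know what effect the study could have detected, and the paragraph cannot say.

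**Working it through.** **1. Passages side by side**

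| | Power Analysis | Planned stepped wedge analysis |
|---|---|---|
| Event | referral or retention, as one composite | referral |
| Rate input | retention, 5% to 85% | no referral rate given |
| Women | those with low utilisation | all women seen by study providers |
| Shape of effect | proportional to length of retention | on/off at the PCP's first template use |

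**2. Can 8.78 be reproduced?** Alpha is 0.05 (sidedness not stated), K = 4, ESV = 0.05 and J = 8.78 PCPs per site. The plan gives no control rate, target effect or PCP-level variance for referral. I used a standard multisite cluster formula on the log-odds scale as a stand-in. It has half the PCPs in each condition and no stepped wedge time structure:

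λ = K·d² / [ESV + 4(τ + s²/n)/J], referred to an F distribution with 1 and K − 1 = 3 degrees of freedom, two-sided 0.05.

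- d is the difference in log-odds between conditions.
- s² is the mean of 1/[p(1 − p)] over the two conditions.
- τ, the between-PCP variance, is taken from the plausible interval: τ = [(logit 0.85 − logit 0.05)/(2 × 1.96)]² = [(1.735 + 2.944)/3.92]² = 1.42. This is a latent correlation of 1.42/(1.42 + 3.29) = 0.30.

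Power 0.80 needs λ = 18.1. With d unstated, 8.78 and 0.80 can be neither confirmed nor refuted. One can only solve for the effect they would imply.

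**3. Implied effects under the two readings of 260.** As a total, 260/(4 × 8.78) = 7.4 women per PCP. The control rates are the lower end of the interval (5%) and its log-odds midpoint (about 35%).

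| Reading of 260 | From 5%, 0.80 needs | From 35%, 0.80 needs | Power for those effects with 222 to 500 women per PCP |
|---|---|---|---|
| per PCP | 24% | 77% | about 0.80 |
| total | 41% | 83% | 0.92 to 0.97 |

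Check of the first cell: d = 1.809, s² = 13.24, and λ = 4 × 3.271/[0.05 + 4(1.425 + 0.051)/8.78] = 13.08/0.722 = 18.1.

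The range 222 to 500 is 2000/9 to 2000/4, from the panel minimum in Site Selection. These are panel sizes, not counts of women seen. Other model variants (fixed site effects, or τ left out) lower the rate needed from 5% to about 9% to 24% on the per-PCP reading and 23% to 41% on the total reading.

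**4. How much the rate input matters.** Take n = 260 per PCP and an assumed rise from 20% to 30%. Then d = 0.539, d² = 0.2905, s² = 5.51 and s²/n = 0.021.

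- Retention interval (5% to 85%), τ = 1.425: λ = 1.162/[0.05 + 4(1.446)/8.78] = 1.162/0.709 = 1.64; power 0.15.
- Assumed referral interval (10% to 40%), τ = (1.792/3.92)² = 0.209: λ = 1.162/[0.05 + 4(0.230)/8.78] = 1.162/0.155 = 7.5; power 0.47.

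The base rate matters as well. With τ = 1.425 and n = 260 per PCP, a 10-point rise has power 0.49 from 5%, 0.15 from 20% and 0.11 from 50%.

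**5. What 260 could be.** Read literally, patients clustered within PCPs may mean 260 per PCP. That fits 2000/8 = 250 to 2000/4 = 500 women per PCP. Read as a total, it equals 4 x 65, the survey target. Survey women enter only after template activation or Gateway attendance, so on that reading they cannot stand for the control-period women whom the model compares.

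**The case against.** Several points on the other side have force.

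- **Referral is the named outcome, and retention in services is among the project's stated goals.** This stands. A reader might infer that power was computed for an unrelated endpoint, but the text does not support that. The mismatch lies in the rate input, the composite event and the retained-longer assumption.
- **260 is attributed to prior work, not to survey enrolment, and may be per PCP.** This also stands. A reader might infer that 260 is the survey count. The match with 4 x 65 makes that possible, but the paragraph never says so. On the per-PCP reading, the patient number already fits an analysis of all women.
- **If 260 is a total, analysing all women adds information.** Correct: power for the same effect rises (step 3). The patient number therefore shows no shortfall.
- **An interval of 5% to 85% is wide enough to hold most referral rates, and a wide interval may be cautious.** Possibly. However, its width sets the variance in step 2, and nothing in the plan ties it to variation in referral between PCPs. Without a target effect, caution cannot be shown either.
- **The calculation also seeks a minimum number of exposed patients, and section 5.5 collects enrollees' service use from six months before the intervention.** Both are true. Enrollees do have earlier data, but these are utilisation histories of women selected by later exposure, not the referral data on all women seen.

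None of this supplies a referral rate among all women or removes the low-utilisation label.

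**Conclusion.** The concern holds for the rate input and the wording around it. The 0.80 power with nine PCPs per site is not established for referral among all women seen. The ambiguity of 260 is a second, smaller defect: it needs stating, and it becomes a population mismatch only if 260 is a total.

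A reader might go further and infer that the study is underpowered. The documents do not support that, because the direction of the error cannot be determined. In the illustration, replacing the interval moves power from 0.15 to 0.47 for one effect, and changing the base rate moves it from 0.49 to 0.11 for the same 10-point rise. Those figures rest on the stand-in formula, on taking the between-PCP variance from the interval, and on assumed referral rates. They show sensitivity and do not estimate this study's power. The textual mismatch needs none of those assumptions.

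**What to change.** In the Power Analysis paragraph of section 5.6:

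1. Replace the retention/low-utilisation input, the composite event and the retained-longer assumption with a binary referral outcome per woman seen.
2. Restate power, or the detectable effect, using the pre-launch referral rate from CDW, a stated target effect, women seen per PCP in control and in intervention periods, and PCP and site variances for referral.
3. Say whether 260 is per PCP or a total.

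If this is not done, withdraw the 0.80 claim for the referral analysis.

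The cost is one recalculation and a paragraph of wording, with no extra enrolment. The restated figure may be more or less favourable than 0.80.

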**Project Methods:** The CV toolkit will be implemented at four women's health clinics over two years. The CV toolkit includes four components: (1) Patient education/activation tools, such as informational posters and fliers about women's CV risk (2) a CV risk assessment computerized template, which systematically captures CVD risk factor history and data from patients' medical records, and provides open fields for the provider to enter any relevant information from the patient's CV worksheet (worksheet captures CVD risk of patient and family history), (3) provider information and education programs as well as referral tools to internal services (e.g., women's MOVE! Program, smoking cessation clinics, dieticians, health coaches, pharmacists and CV or mental health specialists as needed), and (4) the Gateway to Healthy Living program tailored to Women Veterans, a facilitated group meeting that occurs in a structured format with personalized goal setting and identification of key services available at the local site to assist with lifestyle changes necessary for patient-targeted CV risk reduction. We will conduct baseline and post-implementation surveys and/or interviews with 260 patients (65 per site) as well as pre-, mid-, and post-implementation non-human subjects research interviews with 60 staff (15/site).

**Results:** The project is currently in the pre-implementation phase at the first site (GLA) which includes the activities from Component A (non-human subjects research interviews with staff). We have also recruited the second site and will begin pre-implementation work once the site application (LSI) is approved.

**Anticipated Impacts on Veterans' Healthcare:** The proposed toolkit is designed to promote patient-centered decision-making and effective clinical action around CV risk reduction among women Veterans and their VA primary care providers. Toolkit implementation and spread should ultimately reduce persistent gender disparities in quality and outcomes of VA care.

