## Site Selection, CV Toolkit, and REP Implementation Phases

The CV toolkit will be implemented at four VA facilities with moderately large panels of women Veterans. WH clinics are eligible if they have PC panels of women patients that total at least 2000+ women and they have at least 4-8 PCPs per site whose panels include at least 100 women Veterans and women comprise at least 10% of the provider's patient panel. Currently, two sites have been selected for implementation and two other sites will be added to our protocol at a future date. Our first site where we will launch the CV toolkit is GLA, where the PI ([name]) is the PBRN Site Lead. Our second site has now been recruited (West Haven) and their site application will be submitted to CIRB shortly. All site selection will be done in collaboration with [name], Director of the VA WH-PBRN, and member of our Strategic Advisory Group ([name] LoS).

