## **Risk to Subjects**

This study involves both Veteran (260 total across four sites) and VA Staff participants (60 total across four sites).

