**Quantitative Analysis:** We will use descriptive and inferential statistics to understand variations in the measures described above. For patients, we will conduct bivariate analysis to examine variations in outcomes (CV risk factor control, cardiac event or procedure, etc.) by those who participated in the *Gateway to Healthy Living* program, versus those who received a referral to a different program/service, and those who received no referral. For providers, we will examine differences in their patient panel (e.g. those with CV risk factors under control at follow-up) by their engagement in the CV toolkit program. To evaluate the CV toolkit, we will use the nonrandomized stepped wedge design, a generalized mixed model coupled with an allowance for nonrandom effects, to evaluate the implementation across the providers at four sites. The intervention will be defined as “turning on” when a provider first engages in the CV toolkit (first

uses the CV template). We will model the effect of the implementation of the CV toolkit intervention on referral rates, while controlling for organizational level, provider level and patient level covariates.

**Impact-focused evaluation:** Secondary aims focus on factors that empower Women Veterans to engage in and benefit from care. We will use generalized linear mixed models (GLM) to evaluate a) cross-sectional relationships of patient activation, health-related quality of life, and care experiences at enrollment, with provider and site characteristics, adjusting for patient social and demographic characteristics; and b) prospective changes in patient activation, health-related quality of life, and care experiences from enrollment to 6-month follow-up, adjusting for patient, provider, and site characteristics. We will also construct multi-level mediation and moderation models to explore whether engagement-related factors such as patient activation, strength of treatment preferences, or the communication subscale of the CAHPS are associated with greater benefit from or satisfaction with care.

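### The stated 0.80 power needs 9 template-using PCPs per site, and the site-selection minimum of 4-8 PCPs does not secure that number

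*Combined protocol and SAP*

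**What the plan says.** Section 5.6, Power Analysis, sets out to find how many providers must turn the intervention on, described as "the number of PCPs who use the CV template". Its answer is "we need at least 8.78 (rounded to 9) referring PCPs per site to achieve power at 0.80". The inputs listed are alpha 0.05, four sites, an effect size variability of 0.05, a plausible range of 5% to 85%, and at least 260 for the "sample size of patients clustered within referring PCPs". Section 5.6, Quantitative Analysis, starts the intervention "when a provider first engages in the CV toolkit", meaning at the first use of the template.

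The site-selection text in section 5.1 makes a women's health clinic eligible if its primary care panels total at least 2000 women and "they have at least 4-8 PCPs per site whose panels include at least 100 women Veterans", with women at least 10% of each such panel. Two sites have been chosen; the text adds that "two other sites will be added to our protocol at a future date".

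The Abstract describes "surveys and/or interviews with 260 patients (65 per site", and Risk to Subjects says "This study involves both Veteran (260 total across four sites". There, 260 is the survey total. Section 5.1 measures referrals in all women seen, not only in those surveyed.

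**The concern.** The power statement and the site rule both concern PCPs per site, but they do not meet. The minimum in 5.1 is a range, so it is unclear which number admits or rejects a clinic. Neither 4 nor 8 reaches 9. The rule also counts PCPs with qualifying panels, whereas 5.6 counts PCPs who use the template. Section 5.6 plans to compare frequent with infrequent template users, and section 5.1 expects sites to adopt at different rates, so uptake cannot be taken as complete. The documents give no PCP count for any site, no expected number of users, and no step to take if fewer than 9 turn on.

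The only power figure for the stepped-wedge referral analysis is at stake, while two of the four sites are still to be chosen under this rule.

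**Working it through.** **Counts.** Required: 9 × 4 = 36 template-using PCPs. At the floor of the site rule: 4 × 4 = 16 to 8 × 4 = 32 qualifying PCPs, before any non-use. The 2000-woman requirement does not close the gap: 8 PCPs averaging 2000/8 = 250 women, or 4 averaging 2000/4 = 500, would meet it. Nor do the 15 staff per site, an interview sample that mixes PCPs with nurses, clerks and administrators.

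**The plan's own figure.** 8.78 cannot be derived from the stated inputs, because 5.6 gives neither a PCP-level ICC nor a target difference in referral rate, and the meaning of 260 is unclear. Assumed values can land close to it: with random sites, 65 patients per PCP, ICC 0.05 and a standardised effect of 0.60, the parallel formula below gives 8.76. The figure is not shown to be wrong and is taken as given here.

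**Size of the loss.** Let K = 4 sites, J users per site, n patients per user, ρ the PCP-level ICC and ESV = 0.05. With sites random, the test is F with 1 and K − 1 = 3 degrees of freedom at alpha 0.05, and λ = K·d²/V(J).

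- Parallel comparison of PCPs: V(J) = 0.05 + 4[ρ + (1 − ρ)/n]/J.
- Within-PCP crossover (equal patients before and after, a stable PCP effect that cancels, no period effects): V(J) = 0.05 + 4[(1 − ρ)/n]/J.

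Power 0.80 needs λ = 18.11. Fixing d so that this holds at J = 8.78 gives λ(J) = 18.11 × V(8.78)/V(J). ICC is assumed to be 0.01-0.30. The range for n runs from 100, the minimum qualifying panel in 5.1, to the 260 of 5.6 read as per PCP.

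Example, n = 100 and ρ = 0.10:

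- Parallel: V(8.78) = 0.05 + 0.436/8.78 = 0.0997; V(4) = 0.05 + 0.436/4 = 0.159; λ = 18.11 × 0.0997/0.159 = 11.4; power 0.62.
- Crossover: V(8.78) = 0.05 + 0.036/8.78 = 0.0541; V(4) = 0.05 + 0.036/4 = 0.059; λ = 18.11 × 0.0541/0.059 = 16.6; power 0.77.

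Over the whole assumed range:

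| Users at every site | Parallel | Crossover, no period effects |
|---|---|---|
| 4 | 0.56-0.75 | 0.77-0.79 |
| 6 | 0.69-0.78 | 0.79-0.80 |
| 8 | 0.78-0.80 | 0.80 |

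In the parallel model, two sites at 9 and two at 4 give 0.70-0.78. Two at 12 and two at 8 give 0.80-0.83, so there is no loss.

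**Uptake.** To have 9 users, a site needs 9/0.9 = 10 PCPs at 90% uptake, 9/0.8 = 11.25 (so 12) at 80%, and 9/0.5 = 18 at 50%. These uptake rates are illustrations; the documents give none.

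**The case against.** A reader might infer that the two sections contradict each other. They do not. An eligibility floor and a power requirement are different statements, and a clinic above the floor may have 9 or more users. The two counts also cover different groups: PCPs with fewer than 100 women may use the template, so 16-32 against 36 is not like for like. Section 2.0 mentions two women's primary care clinics at GLA, so a site need not be small.

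A reader might also infer that the study will be underpowered. The documents do not support that either, since no site is shown to have fewer than 9 users. The low figures at 4 PCPs come from a parallel model, whereas the stepped-wedge text in 5.1 makes sites their own controls and 5.6 turns each provider on at first use. With that crossover the same formula loses 1 to 3 points at 4 PCPs. In the other direction, period effects or drifting PCP effects would enlarge the loss, and the power paragraph itself describes patients clustered in PCPs with treatment at that level, so the parallel reading cannot be dismissed.

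Finally, 5.1 assesses the primary implementation outcomes by stakeholder interviews, which limits the weight of the referral power. All of this stands. None of it supplies the missing count or uptake assumption.

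**Conclusion.** The point holds in limited form: the site rule does not secure the 0.80 stated in 5.6. The comparison of 4-8 with 9 needs no model and is firm. The size of any loss is not known. It is negligible to small if the minimum means 8. If it means 4 at every site, it ranges from a point or so (crossover without period effects) to about 24 points (0.80 − 0.56, parallel, ICC 0.30). Those figures rest on taking 0.80 at 8.78 as correct, on the assumed ICC and patients per PCP, and on random site effects. The matter should be fixed, but at low priority.

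**What to change.** In 5.6, redo the calculation for the planned crossover analysis. Restate power for the number of template-using PCPs expected at the four sites, under a stated uptake assumption, with lines for 4, 8 and 9 users per site. Give the inputs that the calculation needs: the PCP-level ICC, the detectable difference in referral rate, and whether 260 is patients per PCP or the survey total.

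In 5.1, replace the range with a single figure reconciled with the restated power, or keep the site rule and report the lower power. A single panel-based figure alone would still not count template users, so the uptake assumption is needed in either case.

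The cost is one recalculation, a revised paragraph in 5.6 and, if chosen, a changed eligibility figure in 5.1. The stated power may become slightly less favourable. A higher minimum could narrow the pool for the two sites still to be added and would have to be checked against the two already selected. No extra patients or sites are required.

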#### Nonrandomized Stepped Wedge Study Design for Implementation Trials.

The CV Toolkit project will use a nonrandomized stepped wedge design, which rely on sequential roll-out to participating sites over time, while using other sites as controls until they begin implementation. Consistent with our substantial prior experience using these designs in VHA and armed with complexity theory's recognition of nonlinearity of implementation, we will use *nonrandomized* stepped wedges (rather than randomized) given their suitability for studying implementation. This design acknowledges that sites are heterogeneous, face multiple constraints, and, as a result, are ready to adopt interventions at different rates. The modified design explicitly considers the timing of implementation spread and addresses the statistical issues introduced by lack of randomization in implementation starts and processes. We will analytically compensate for the design by collecting patient-, provider-, and site-level data that may be associated with timing of the adoption of each intervention. We will include three levels in our hierarchical nonrandomized stepped wedge models: (1) patient, (2) time of intervention (i.e., when a provider starts using the intervention), and (3) site. Outcomes of interest (e.g. referrals to Gateway, other health promotion program and/or specialist) are measured for all patients at each site within the given intervention time period.

Nonrandomized stepped wedge designs make efficient use of all data available for within-site and between-site comparisons. For the within-site comparison, sites act as their own controls in an evaluation that compares sites pre- versus post-implementation. The comparison examines sites as they cross-over from control to intervention states. The between-site comparison evaluates the intervention period for a site vs. all other intervention and control periods for all sites. By having these two types of comparison, the design improves on the validity of the

evaluation of the intervention, by accounting for historical time trends that may occur outside of the intervention and for site contextual characteristics that may affect site performance.

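### The 0.80 power assumes an effect that grows with time, but the described analysis tests an on/off switch on referral, so the figure does not apply to that test

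*Combined protocol and SAP*

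**What the plan says.** All places are in the Combined protocol and SAP.

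- **Section 5.6, Power Analysis.** The calculation is for a three-level model with 4 sites, at least 260 patients, alpha 0.05 and an effect size variability of 0.05. It arrives at 8.78, rounded to 9, referring PCPs per site for power 0.80. The outcome is described thus: "The outcome is binary (referred/retained vs. not), and measured at the patient level (Level 1". The plausible range of 5% to 85% is for "Retention among those with low utilization". The effect shape is stated as: "Our power analyses assume that the treatment effect is linear over time, i.e. patients that are retained longer have proportionally better outcomes". The section then refers to sensitivity analyses but shows no results.
- **Section 5.6, Power Analysis, level of the effect.** "Treatment effect is measured at Level 2, i.e., timing of when the PCPs turn on".
- **Section 5.6, Quantitative Analysis.** The intervention turns on "when a provider first engages in the CV toolkit", meaning at first use of the template. The aim of the model is: "We will model the effect of the implementation of the CV toolkit intervention on referral rates". It is a generalized mixed model with organisational, provider and patient covariates.
- **Section 5.1, Nonrandomized Stepped Wedge Study Design.** On the within-site contrast: "The comparison examines sites as they cross-over from control to intervention states". The design is credited with "accounting for historical time trends that may occur outside of the intervention".

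The plan gives no model equation, no term for time since first use, and no form for calendar time.

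**The concern.** The power statement and the analysis describe two different effects. One is graded, increases with time and is worded in terms of how long patients are retained. The other is a change of state at a provider's first template use, measured on referral. A power figure belongs to one effect in one model, so 0.80 for the first says nothing definite about the second.

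The mismatch could also affect the estimate. In a stepped wedge with calendar adjustment, sites that have already switched serve as comparators for sites that switch later. If the effect in those early sites is still growing, the calendar terms absorb part of the growth and the single on/off coefficient shrinks. A toolkit that works gradually could then look weak. This model is how Aim 3 evaluates the toolkit.

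**Working it through.** **1. The plan's own figure.** The 8.78 cannot be reproduced, because the plan states no control and intervention referral rates and no intraclass correlation. I back-solved instead, on the logit scale.

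- PCP variance from the 5% to 85% range: logit(0.85) = 1.735 and logit(0.05) = -2.944, so tau = [(1.735 + 2.944) / (2 x 1.96)]^2 = 1.42.
- Variance of the effect: [ESV + 4(tau + s2/n)/J]/K, with ESV = 0.05, J = 8.78, K = 4, s2 the patient-level variance and n patients per PCP. Alpha is taken as two-sided.
- With 65 to 260 patients per PCP, power 0.80 would need an odds ratio of about 6.0 to 6.6 (random sites) or 3.3 to 3.5 (fixed sites). At n = 260 and a 35% control rate, that is 35% to 77% or 35% to 64%. The plan states none of these effects.

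**2. What an on/off coefficient returns if the effect grows.** Inputs from the plan: a 15-month implementation phase, with the first site starting late in Year 2, the second at the start of Year 3, and two more in Years 3 to 4 (section 5.1). The six-month look-back is in section 5.5. My assumptions are:

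- site starts at months 18/24/30/33 or 18/24/30/36;
- 6 PCPs per site and monthly cells;
- an effect rising linearly from first use to D at month 15, without noise.

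If all PCPs start with their site, the true average is the mean of 1/15, 2/15, ..., 15/15, which is 8/15 = 0.53 D. With PCP starts spread over 6 months (lags 0, 1, 2, 4, 5, 6) it is 0.45 D.

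I fitted least squares with PCP effects, month effects and one on/off term. I then added months since first use and compared the standard error of the resulting average effect with that of the on/off term (independent errors).

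| Data window | PCP starts | True average | On/off estimate | SE ratio |
|---|---|---|---|---|
| All sites from month 12 to own month 15 | together | 0.53 D | 0.14 to 0.17 D | 1.18 to 1.23 |
| Same | spread | 0.45 D | 0.21 to 0.24 D | 1.10 to 1.12 |
| Each site from -6 to +15 months only | together | 0.53 D | -0.15 to -0.16 D | 3.8 to 4.2 |
| Same | spread | 0.45 D | -0.04 to -0.05 D | 1.6 |

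With the common look-back, the on/off term recovers between 0.14/0.53 = 0.26 and 0.24/0.45 = 0.53 of the average. Under a constant effect it returns 1.00 of the truth in every row.

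**3. A mixed-model version.** This used 9 PCPs per site, quarterly periods, PCP variance 0.02 to 0.10, site variance 0.005 to 0.05 or fixed sites, and cell sizes 0.5 to 50. The slope was set so that a matching linear-exposure model has power 0.80. The ranges cover several assumed schedules.

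| Calendar term | On/off estimate / true average | Power of on/off test |
|---|---|---|
| Included | -0.16 to 0.84 | 0.00 to 0.51 |
| None | 0.87 to 1.00 | 0.49 to 0.62 |

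No scenario reached 0.80. With provider-by-provider starts and calendar adjustment the ratio was 0.02 to 0.84, so there was shrinkage but no reversal.

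**4. Does a step plus a slope cure it?** Only if the shape is right. If the effect instead plateaus at month 4 (18/24/30/33, PCPs starting together), the true average is 0.90 of the plateau. Step plus slope gives 1.22 with site-only windows and 0.92 with the common look-back.

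**The case against.** **The single step is inferred.** The plan gives no coefficient structure. Section 5.1 makes the second level the time at which a provider starts, and the Power Analysis speaks of timing, which leaves room for a time term. This stands: a single step is the natural reading, not a stated one. It does not rescue the power figure, because no such term is written down.

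**The linear sentence is about patients, not providers.** It speaks of patients retained longer, whereas my calculation lets the effect grow with months since the provider's first use. This also stands. The shrinkage is conditional on that interpretation; the mismatch between power and analysis is not. The contrast between retention and referral is softer than it looks, since the power section also names referrals and codes the outcome as either.

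**Sensitivity analyses are cited.** No results are shown, and the claim made for them concerns detection, not an unbiased step estimate.

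**Stronger readings.** A reader might infer that the main estimate will have the wrong sign. The documents do not support that. The negative values depend on calendar adjustment and, in the fixed-effects fits above, on site-only windows. The six-month look-back behind those windows is described for enrollees' records. For the roll-out, section 5.1 describes data on all women seen by study providers at all sites over the study period, and with that common look-back every value in the first table of step 2 is positive. A reader might also look for one replacement power figure. None can be given, because the plan states no effect size.

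**Conclusion.** The mismatch is real and rests on the text alone: the 0.80 at 9 PCPs per site is tied to an effect linear in time, and the described test is a switch on referral. The figure should not be quoted for that test.

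The consequence for the estimate is conditional. If the effect grows with time since first use and calendar time is adjusted for, the on/off coefficient recovers roughly a quarter to a half of the average effect with a common look-back. In some other windows it is near zero or slightly negative. Without a calendar term the shrinkage is small, but dropping it would undo a stated strength of the design. Under a constant effect there is no bias. Site starts, the linear shape, PCP spread and variances are my assumptions.

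This should be corrected. It does not show that the planned analysis must fail.

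**What to change.** 1. **Power Analysis (section 5.6).** Withdraw the 0.80, or restate it for the referral effect that the Quantitative Analysis will estimate. State the control and intervention referral rates and the PCP and site intraclass correlations. Remove the linear-retention assumption or justify it.
2. **Quantitative Analysis (section 5.6).** Write the model equation. Use referral data for all study PCPs at all four sites from a common calendar start. Include calendar-time terms, and add time since the PCP's first template use to the step. Report the average effect over the 15-month on-period as the main estimate. Give the on/off model and one other shape, such as a plateau or quarter-since-use indicators, as sensitivity analyses.

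**Cost.** New wording and one new power run. The all-provider referral data are already planned in section 5.1. With the common look-back the standard error rises by about 10 to 25%; with site-only windows it is 1.6 to 4.2 times as large, so the model change should go together with the common window. The estimate will depend on the assumed exposure shape and should not be presented as exact. The stated power will probably fall.
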